If [name] or [name] are notified of a patient at risk for suicidal behavior, [name] will contact that patient, verify their response and decide if a wellness check from police is needed or other interventions. That patient will be offered immediate assistance, including calling an

ambulance for transport to the Emergency Department, and their primary physician will be informed.

Randomization

Only Investigational Drug Services (IDS) Pharmacy will be aware of drug allocation prior to completion of data collection for the randomized, placebo-controlled study. A computer-generated randomization scheme will be used to randomize participants to receive either ketamine or saline (allocation ratio 1:1, blocks of 4). The study participants, intraoperative anesthesiologists, and study staff conducting postoperative assessments will be blinded to drug allocation until data collection is completed.

Infusions

The study intervention will occur during surgery (Study Day 0). Participants will be randomized to one of two groups: Group A (n=20) will receive a ketamine infusion of 0.5 mg/kg over 40 min during surgery, beginning after anesthetic induction with propofol. Group B (n=20) will receive a saline infusion over 40 min during surgery, beginning after anesthetic induction with propofol. Infusion (instead of bolus) dosing of ketamine was chosen since infusions have demonstrated antidepressant efficacy in outpatient psychiatric populations, as well as theoretically lower risk of adverse events due to lower peak serum concentrations compared to bolus dosing. A patient who is **not** enrolled in the study has a reasonable chance of receiving the same treatments (ketamine or saline) at comparable doses as those tested in the study.

Monitoring

Routine vital signs will be collected before and after surgery by the participant's nurse and reviewed by investigators. Each participant will have continuous physiological monitoring during their anesthetic. A SedLine® Brain Function Monitor will be used to evaluate depth of anesthesia/sedation. If the participant experiences an adverse event temporally related to the infusion where corrective action by the intraoperative anesthesiologist requires unblinding, then the study infusion drug will be revealed to the anesthesiologist.

Data Collection Procedures

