- Adverse Events Review
- Montgomery-Asberg Depression Rating Scale (MADRS)

By the Participant, reviewed by Investigators:

- Hospital Anxiety and Depression Scale (HADS)
- Brief Pain Inventory (BPI)

Day 7 (inpatient or via phone):

By Physician or Study Staff:

- Vital Signs (inpatient only)
- Concomitant Medication Review
- Adverse Events Review
- Montgomery-Asberg Depression Rating Scale (MADRS)

By the Participant, reviewed by Investigators:

- Hospital Anxiety and Depression Scale (HADS)
- Brief Pain Inventory (BPI)

Day 14 (inpatient or via phone):

By Physician or Study Staff:

- Ask participants what treatment they believe they received
- Reveal treatment to participant
- Vital Signs (inpatient only)
- Concomitant Medication Review
- Adverse Events Review
- Montgomery-Asberg Depression Rating Scale (MADRS)

By the Participant, reviewed by Investigators:

- Hospital Anxiety and Depression Scale (HADS)
- Brief Pain Inventory (BPI)

Participant Compensation:

• \$50 after completion of all study assessments

Study Procedures Matrix

	Screen- ing	Day 0 (Baseline)	Day 0 (Intraop)	Day 1	Day 2	Day 3	Day 5	Day 7	Day 14
PHQ-8	Х								
Inclusion/Exclusion Criteria	Х								
Demographic data	Х								
Consent	Х								
Concomitant Medication Review	X	Х		Х	Х	Х	X	Х	х
Medical and Psychiatric History	X								
Physical Exam	Х								
Vital Signs	X	Х		Х	Х	0	0	0	0
Continuous physiological monitoring			Х						
Urine toxicology screen test	Х								
Labs and studies as warranted by standard preoperative medical clearance (includes pregnancy test)	Х								
Mini International Neuropsychiatric Interview (MINI) - A , I & J	х								

Hospital Anxiety and Depression Scale (HADS)	×	x		x	x	x	X	х	х
Montgomery Asberg Depression Rating Scale (MADRS)	X	Х		X	X	X	X	X	х
Columbia Suicide Severity Rating Scale (CSSRS) – Short Screen	x								
Maudsley Staging Method (MSM)	Х								
Brief Pain Inventory	Х	Х		Х	Х	Х	Х	Х	Х
Randomization	Х								
Ketamine infusion or Placebo (saline) infusion			×						
SedLine® Brain Function Monitor			Х						
Ask participants what treatment they believe they received									Х
Treatment revealed to participant									Х
Participant compensation	X								х

X – required

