This is a single-site phase IV randomized clinical trial utilizing a quadruple-masked, placebo-controlled, parallel arm design. Participants will be randomly allocated in a 1:1 ratio to one of two groups: Group A (n=20) will receive a ketamine infusion of 0.5 mg/kg over 40 min during surgery. Group B (n=20) will receive a saline infusion over 40 min during surgery. In both groups, the study drug will be given after anesthetic induction. The participants, care providers, investigators, and outcomes assessors will be masked.

10. Randomization

Participants will be sequentially randomized as they enter the study. We will employ block randomization with 5 blocks of 8 patients each.

11. Sample size

We will enroll a total of 40 participants. Our sample size calculation was derived from an *a priori* power analysis for the primary outcome measure with a 1:1 allocation ratio. In a randomized controlled trial of ketamine vs active placebo (midazolam) performed by

Phillips et al. (2019), participants had a mean decrease of 10.9 points (SD=8.9) in MADRS total score relative to pre-infusion scores compared with a mean decrease of 2.8 points (SD=3.6) with midazolam. Using these results, we computed an estimated total sample size of 38 participants at a two-sided alpha level of 0.05 and 80% power. An additional 2 participants were added to account for potential attrition, for a total of 40 participants. Given the increased statistical efficiency of mixed models for repeated measures (MMRM) compared to parametric pre-post tests, we assumed that 40 participants should be sufficient to power our study for MMRM analysis.

12. Framework

We plan to evaluate the antidepressant superiority of ketamine to placebo by assessing the postoperative MADRS scores from postoperative Day 1 through Day 3. Additional outcomes collected at postoperative Day 5, 7, and 14 will be used for statistical model building and exploratory analyses.

13. Interim data monitoring

13a. Statistical interim analyses planned and time points

No statistical interim analyses planned.

13b. Any planned adjustment of significance level due to interim analysis

N/A.

13c. Details of guidance for stopping the trial early

N/A.

14. Timing of final analysis

Once all data have been collected at all planned time points from the final (40th) participant, all investigators will be unmasked and all outcomes will be analyzed together in the final analysis.

15. Timing of outcome assessments

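### The documents conflict on block size (4 or 8) and on when treatment is revealed; if it is revealed patient by patient at Day 14, either fixed block makes some later allocations deducible

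*Protocol*

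**What the plan says.** **Block size.** Protocol section 8D, Randomization, gives "allocation ratio 1:1, blocks of 4". SAP section 10 states "We will employ block randomization with 5 blocks of 8 patients each". SAP section 4b explains two changes between SAP versions (the endpoint window and the outcome scale); neither concerns randomization, so the difference in block size is unexplained.

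**One list.** The trial has a single site. SAP section 10 says "Participants will be sequentially randomized as they enter the study". Neither document describes stratification, varying block sizes, or withholding the block size from enrolling staff.

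**Masking until the end.** Protocol section 8D says "Only Investigational Drug Services (IDS) Pharmacy will be aware of drug allocation prior to completion of data collection for the randomized, placebo-controlled study", and that "study staff conducting postoperative assessments will be blinded to drug allocation until data collection is completed". SAP section 14 likewise unmasks investigators only after the 40th participant's data are in.

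**Disclosure at Day 14.** The protocol's Day 14 task list, under the heading for physicians or study staff, includes "Reveal treatment to participant". This stands above that day's MADRS in the list. The Study Procedures Matrix marks the step as required in the Day 14 column, and places randomization in the screening column.

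**The concern.** In a balanced block, every disclosed allocation narrows those that remain. Once half the block is known to have gone to one arm, the rest must go to the other. Concealment with fixed blocks therefore depends on earlier allocations staying hidden, and the Day 14 schedule provides for each of them to be disclosed in turn while recruitment continues.

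Two things would be at stake. First, selection: eligibility includes investigator judgment (likely compliance, suicide risk, interfering physical conditions) and a threshold that contains a staff-rated MADRS score. Second, rating: the primary outcome is a clinician-rated scale on Days 1 to 3, and the schedule uses the same generic staff heading for screening, for those ratings and for the Day 14 reveal. No rule separates these tasks.

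**Working it through.** **1. The plan's own layout.** 5 × 8 = 40, which matches the total in SAP section 11. Blocks of 4 also fit (10 × 4 = 40), so the total does not show which size is in use. The documents give no figure for predictability.

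**2. Ceiling: every earlier allocation in the block is known.** An allocation is certain when one arm of the block is already full.

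- Blocks of 4: positions 1 and 2 are never certain. Position 3 is certain when the first two match (probability 1/3). Position 4 is always certain. Expected number: 1/3 + 1 = 4/3 per block; (4/3)/4 = 33.3%, or 10 × 4/3 = 13.3 of 40 patients.
- Blocks of 8: positions 5 to 8 are certain with probability 1/35, 5/35, 15/35 and 35/35. The sum is 56/35 = 1.6 per block; 1.6/8 = 20.0%, or 8 of 40 patients.
- Both agree with the general result 2/(b + 2) for block size b.
- A best guess under full knowledge is right 70.8% of the time (blocks of 4) or 66.6% (blocks of 8), against 50% by chance.

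**3. Disclosure with a lag.** Inputs:

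- Lag: 14 days, taking randomization to be on the day of surgery.
- Accrual (assumption): SAP section 4c puts the revision at 75% of target enrolment, so 0.75 × 40 = 30 patients. SAP versions 1.0 and 2.0 are dated 10/21/2019 and 10/28/2021, 738 days apart. 738/30 = 24.6 days per patient, about 1.24 per month. The documents state neither a start date nor a rate, so a range is shown.

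With exponential gaps of mean g, lag L and x = L/g, the chance in blocks of 4 that position 3 is certain is e^(−x)/3. For position 4 it is [e^(−x)(1 + x) + 2e^(−x)]/3. Adding these and dividing by 4 gives a share of e^(−x)(4 + x)/12. At x = 0 this is 4/12 = 33.3%, as in step 2. At x = 14/24.6 = 0.569 it is 0.566 × 4.569/12 = 21.5%. A simulation of 10,000 trials of 40 patients gives the same figure and supplies those for blocks of 8:

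| Patients per month (14-day lag) | Blocks of 4 | Blocks of 8 |
|---|---|---|
| 0.5 | 28.1% | 17.3% |
| 1 | 23.4% | 14.9% |
| 1.24 | 21.5% | 14.1% |
| 2 | 16.3% | 11.0% |
| 3 | 11.3% | 8.3% |
| 6 | 3.6% | 3.1% |

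For mean gaps of 12 to 48 days the range is about 13% to 27% (blocks of 4) and 9% to 17% (blocks of 8).

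**4. Longer lag.** The matrix puts randomization at screening, although the protocol also allows screening on the day of surgery. At 1.24 patients per month:

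| Days from randomization to reveal | Blocks of 4 | Blocks of 8 |
|---|---|---|
| 21 | 17% | 12% |
| 28 | 14% | 10% |
| 44 | 8% | 6% |

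**5. No reveal before the end.** If the masking statements govern, no earlier allocation is known and the share is 0% for either block size.

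**The case against.** The strongest reply is that the documents already forbid the leak. The pharmacy alone holds the list, assessors stay blinded until data collection ends, and SAP section 14 unmasks investigators after the last participant. On that reading nothing is predictable. This is a fair reading of those statements, but a required Day 14 reveal cannot be carried out for each participant while they are true. The conflict has to be resolved in the text.

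Several further objections stand as limits on size:

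- The generic staff heading does not show that the person who reveals a treatment also enrols or rates later patients.
- Deduction needs the list positions. Patients randomized at screening who then miss the day-of-surgery threshold or withdraw may use slots that are never revealed.
- With 4 in one document and 8 in the other, someone guessing could apply the wrong size, though this is no safeguard.
- The SAP reports recruitment difficulty during the pandemic followed by wider eligibility, so accrual was probably uneven. Shorter gaps lower the share.
- At 75% enrolment about 10 slots remained. At the assumed rate a new list would protect about two patients (21.5% of 10) or one (14.1% of 10).
- The percentages describe knowledge at enrolment. They do not measure bias in MADRS or in the type I error rate.

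A reader might infer that allocation is simply not concealed for about one patient in five. The documents do not support this. Full disclosure gives one in three with blocks of 4 and one in five with blocks of 8. A figure near one in five with blocks of 4 requires a 14-day lag and an accrual rate that is not stated.

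**Conclusion.** The point holds conditionally. Two contradictions are certain from the text: the block size (4 against 8) and the time of disclosure (end of data collection against each participant's Day 14). The predictability follows from the second and depends on two conditions: that the rolling reveal is carried out, and that enrolling or rating staff learn of it.

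Under those conditions, at most 33% (blocks of 4) or 20% (blocks of 8) of allocations become certain. About 21% or 14% is a reasonable central figure if patients arrive every 24.6 days on average and randomization falls on the day of surgery. It is lower with faster accrual or earlier randomization. If no allocation is revealed before the end, it is zero. The documents do not show that any allocation was in fact deduced, or that any rating was affected. The text should be corrected because the remedy is inexpensive and the primary outcome is rated by a clinician.

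**What to change.** 1. Reconcile Protocol section 8D (Randomization, the Day 14 list and the matrix) with SAP sections 10 and 14. State one randomization scheme and one time of disclosure, with participants told their treatment only after the last participant's data are collected. The participant's guess of treatment can stay at Day 14.
2. Have the pharmacy generate the remaining slots with randomly varying block sizes, and keep the sizes out of text seen by enrolling and rating staff.
3. Report the block size actually used and whether any treatment was revealed before data collection ended.

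The cost is a short amendment and a new list for the open slots. Participants learn their treatment later, and the final arms may differ by one or two patients. Step 1 closes the scheduled route by itself. Step 2 also limits what could be deduced from any occasional unblinding. A bar on disclosers enrolling or rating later patients could be added if a rolling reveal were kept, but it might need extra staff and is unnecessary once disclosure moves to the end.

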5. AIMS AND HYPOTHESIS

A. Aims:

To determine whether intravenous ketamine, when used for its FDA-approved indication to supplement anesthesia, is associated with a measurable antidepressant effect in severely depressed patients undergoing non-cardiac surgeries when compared to placebo (normal saline infusion).

B. Primary Outcome:

We plan to evaluate the antidepressant superiority of ketamine to placebo by assessing postoperative MADRS scores at multiple timepoints. MADRS (Montgomery-Asberg Depression Rating Scale) is a validated measure of depression severity used routinely in antidepressant trials.

C. Secondary Outcomes:

- Proportion of participants with clinical response (defined as a ≥50% reduction in MADRS score from baseline)
- Proportion of participants with remission (defined as a MADRS score of ≤12 on day 14)
- Hospital Anxiety and Depression Scale
- Cumulative inpatient opioid use
- Hospital length of stay
- Average inpatient opioid use per day
- Opioid use at postop day 7
- Opioid use at postop day 14
- Postoperative numeric pain scores
- Postoperative pain interference scores
- Immunological blood markers

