The first 5 patients that meet inclusion/exclusion criteria will be entered into the open-label feasibility study; all will receive a ketamine infusion. All other patients enrolled thereafter will be entered into the double-blind, randomized, placebo-controlled study. The day of surgery will be considered Day 0 of the study. Baseline assessments must be performed before the patient receives any psychoactive premedication (e.g. midazolam, fentanyl, gabapentin, oxycodone). Assessments will be performed either in the hospital or, if the patient has been discharged (typically on postoperative Day 2), by phone.

Participants who remain in the hospital for at least 24 hours post-surgery will be asked to give blood samples for immunological analyses. Two blood samples (10mL for each draw) will be collected from each participant.

Day 0 (Baseline Assessments):

By Physician or Study Staff:

- Vital Signs
- Concomitant Medication Review
- Adverse Events Review
- Montgomery-Asberg Depression Rating Scale (MADRS)
- Collect breath sample #1

By the Participant, reviewed by Investigators:

- Hospital Anxiety and Depression Scale (HADS)
- Brief Pain Inventory (BPI)

Day 0 (During Surgery):

By the Intraoperative Anesthesiologist:

- Ketamine infusion or placebo (saline) infusion
- Continuous physiological monitoring
- SedLine® Brain Function Monitor to evaluate depth of anesthesia/sedation
- Collect breath sample #2, after infusion is complete

Day 1:

By Physician or Study Staff:

- Vital Signs
- Concomitant Medication Review
- Adverse Events Review
- Montgomery-Asberg Depression Rating Scale (MADRS)

By the Participant, reviewed by Investigators:

- Hospital Anxiety and Depression Scale (HADS)
- Brief Pain Inventory (BPI)

Day 2:

By Physician or Study Staff:

- Vital Signs (inpatient only)
- Concomitant Medication Review
- Adverse Events Review
- Montgomery-Asberg Depression Rating Scale (MADRS)

By the Participant, reviewed by Investigators:

- Hospital Anxiety and Depression Scale (HADS)
- Brief Pain Inventory (BPI)

Day 3 (inpatient or via phone):

By Physician or Study Staff:

- Vital Signs (inpatient only)
- Concomitant Medication Review
- Adverse Events Review
- Montgomery-Asberg Depression Rating Scale (MADRS)

By the Participant, reviewed by Investigators:

- Hospital Anxiety and Depression Scale (HADS)
- Brief Pain Inventory (BPI)

Day 5 (inpatient or via phone):

By Physician or Study Staff:

- Vital Signs (inpatient only)
- Concomitant Medication Review

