STATISTICAL ANALYSIS PLAN

Official Title:

Intraoperative Ketamine Versus Saline in Depressed Patients
Undergoing Anesthesia for Non-cardiac Surgery

NCT Number: 03861988

Protocol last edited: 10/28/2021

Statistical Analysis Plan (SAP)

Section 1: Administrative Information

1. Title and trial registration

1a. Title

Intraoperative Ketamine Versus Saline in Depressed Patients Undergoing Anesthesia for Non-Cardiac Surgery

1b. Trial registration number

ClinicalTrials.gov Identifier NCT# 03861988

2. SAP version: 2.0

3. Protocol version: Stanford eProtocol ID 49114, last revision submitted 8/9/21

4. SAP revisions

4a. SAP revision history

10/21/2019 – version 1.0 (originally included in the study protocol)

10/28/2021 – version 2.0 (created a new, separate SAP document)

4b. Justification for each SAP revision

Version 1.0 to 2.0:

- 1) In our original protocol, recruitment was limited to patients with symptomatic depression presenting for hip and knee arthroplasty at Stanford. Patients undergoing this type of surgery have a predictable postoperative course, which guided our primary endpoint selection. We encountered significant difficulties recruiting patients during the COVID-19 pandemic. Therefore, we expanded eligibility criteria by including patients presenting for a wider variety of surgical procedures, which are described in our updated protocol. To account for the likely increased variability of postoperative recovery in this broader population, we updated our primary endpoint to include data from the first 3 days after surgery, instead of only a single day after surgery.
- 2) In our original protocol, the primary outcome measure was defined as the sum of scores from a clinician-administered scale and a self-report scale. During the recruitment phase of our trial, and prior to unblinding, we presented our analysis plan to a panel of statisticians in the Department of Biomedical Data Sciences at Stanford University. The panel recommended that we could improve the interpretability and reduce the variance in our primary outcome by only using one validated measure (rather than a composite score) as our primary outcome measure. Based on this recommendation, we updated our primary outcome measure to only include the clinician-administered scale (the Montgomery-Asberg Depression Rating Scale).

4c. Timing of SAP revisions

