- 2) MME/day, if on opioids (mean, SD)
- 3) Anticonvulsants (n, %)
- 4) Benzodiazepines (n, %)
- 5) Muscle relaxants (n, %)
- 6) Antidepressants (n, %)
- 7) Antipsychotics (n, %)
- 8) Lithium (n, %)
- 9) Prescription sleep medications (n, %)
- 10) Opioid antagonists (n, %)
- 11) Stimulants (n, %)

25c. Surgical characteristics

- 1) Type of surgery
 - a. ENT/OMF (n, %)
 - b. Thoracic (n, %)
 - c. Breast (n, %)
 - d. Plastic non-breast (n, %)
 - e. Spine (n, %)
 - f. Major joint (n, %)
 - g. Other orthopedic/limb (n, %)
 - h. Intraabdominal general surgery (n, %)
 - i. Urologic and gynecologic (n, %)
 - j. Vascular (n, %)
 - k. Transplant (n, %)
- 2) Type of anesthesia
 - a. General anesthesia (n, %)
 - b. Monitored anesthesia care (n, %)
- 3) Intraoperative nitrous oxide (n, %)
- 4) Intraoperative propofol infusion (n, %)
- 5) Intraoperative opioid infusion (n, %)
- 6) Length of surgery (hours, mean and SD)
- 7) Peripheral or neuraxial catheter placed (n, %)

Section 6: Analysis

26. Outcome definitions

26a. Primary outcome

Postoperative MADRS scores from postoperative Days 1 through 3.

26b. Main secondary outcomes

- 1) Proportion of participants with clinical response (defined as a $\geq 50\%$ reduction in MADRS score from baseline).
- 2) Proportion of participants with remission (defined as a MADRS score of ≤ 12 on day 14).

26c. Other exploratory secondary outcomes

- 1) MADRS scores at postoperative Days 5, 7, and 14
- 2) Hospital Anxiety and Depression Scale
- 3) Cumulative inpatient opioid use
- 4) Hospital length of stay
- 5) Average inpatient opioid use per day
- 6) Opioid use at postop day 7
- 7) Opioid use at postop day 14
- 8) Postoperative numeric pain scores
- 9) Postoperative pain interference scores

27. Analysis methods

27a. Analysis of the primary outcome

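### Immunological blood is requested only from participants who actually stay 24 hours, and the two draws are untimed: selection after randomization, probably small in effect, and no assured pre-infusion value

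*Protocol*

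**What the plan says.** Protocol 5C lists "Immunological blood markers" among the secondary outcomes. The sampling rule is in Protocol 8D, Data Collection Procedures: "Participants who remain in the hospital for at least 24 hours post-surgery will be asked to give blood samples for immunological analyses". The next sentence reads "Two blood samples (10mL for each draw) will be collected from each participant". No time is given for either draw. No day's list, from Day 0 to Day 14, contains a research blood draw, and the Study Procedures Matrix has no row for one. The breath samples also lack a matrix row, but the day lists do place them: one at Day 0 baseline and one after the infusion.

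The infusion is given during surgery on Day 0 (Protocol 8D, Infusions). "Hospital length of stay" is a secondary outcome in Protocol 5C and SAP 26c. Protocol 8C, Analysis Plan item 4, compares secondary outcomes by t-tests or chi-squared tests without a covariate, and calls them exploratory. SAP section 26 does not list the immunological markers, and the missing-at-random assumption in SAP section 28 covers the primary outcome only.

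On how many patients would qualify, the documents give one indication: assessments are done, "if the patient has been discharged (typically on postoperative Day 2), by phone".

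**The concern.** Randomization balances the arms as randomized. It does not balance the subset that is still in hospital a day later. If ketamine changes who stays, and if the patients who stay differ in inflammatory markers (larger operations, more pain, more complications), the sampled arms can differ with no effect of ketamine on the markers. Nothing in the SAP handles this. SAP section 20 promises intention-to-treat analysis for all planned outcomes, which cannot be delivered for markers that were never requested from patients who left early.

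The second problem does not depend on ketamine affecting stay. The draws have no times, so the plan does not guarantee a value from before the infusion. Without one, differences between patients that existed before treatment stay in the error term. Eligibility has been widened (SAP 4b: "we expanded eligibility criteria by including patients presenting for a wider variety of surgical procedures"), and SAP 25c now lists 11 categories of surgery, so a baseline value would be useful here.

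**Working it through.** The documents give no sample size, SD or effect size for the markers, so there is no stated figure to reproduce. What follows is an illustration. From the documents: 20 per arm, two-sided alpha 0.05. Power of 80% is borrowed from the primary outcome's calculation. Assumed: the share staying at least 24 hours in each arm, the correlation ρ between marker and tendency to stay (0.3 to 0.7), and the pre/post correlation r of the marker (0.5 to 0.7).

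**Selection.** Suppose a patient stays when a standard normal recovery variable U exceeds a cut-off c set so that a proportion p stays. Then E[U | stay] = φ(c)/p:

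- p = 0.90: 0.1755/0.90 = 0.195
- p = 0.80: 0.2800/0.80 = 0.350
- p = 0.60: 0.3863/0.60 = 0.644
- p = 0.45: 0.3958/0.45 = 0.880

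With no true marker effect, the spurious difference in SD units is ρ × (difference between the arms in E[U | stay]). The difference detectable with 80% power is (1.960 + 0.842) × √(1/n₁ + 1/n₂), by normal approximation.

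| Staying: saline vs ketamine | Sampled | Spurious difference, ρ 0.3 to 0.7 | Detectable difference |
|---|---|---|---|
| 90% vs 90% | 18 vs 18 | 0 | 0.93 SD |
| 90% vs 80% | 18 vs 16 | 0.155ρ = 0.05 to 0.11 SD | 0.96 SD |
| 60% vs 45% | 12 vs 9 | 0.236ρ = 0.07 to 0.17 SD | 1.24 SD |

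The zero in the first row assumes that the same kind of patient stays in both arms. With all 40 patients sampled the detectable difference is 2.802 × √(2/20) = 0.89 SD.

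In the third row the bias is 6% to 13% of the detectable difference (0.071/1.235 and 0.165/1.235). Divided by the standard error √(1/12 + 1/9) = 0.441, it shifts the test statistic by 0.16 to 0.37. A nominal 5% error rate then becomes about 5.3% to 6.6%.

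**Precision.** Adjusting for a pre-infusion value multiplies the variance by 1 − r², which is 0.75 at r = 0.5 and 0.51 at r = 0.7. At 18 vs 16, the detectable 0.963 SD becomes 0.963 × √0.75 = 0.83 SD and 0.963 × √0.51 = 0.69 SD. At 12 vs 9, 1.235 becomes 1.07 and 0.88 SD. These gains are the same whether or not ketamine alters stay.

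A pre-infusion draw alone would not secure them. A t-test on change has variance factor 2(1 − r), which is 1.0 at r = 0.5 (no gain) and 0.6 at r = 0.7 (0.963 × √0.6 = 0.75 SD). The covariate has to be in the analysis.

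**The case against.** The best case for the plan has four parts.

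First, discharge is described as typically on Day 2, so most patients should pass 24 hours. This stands, although the statement sits beside a widened surgical mix and no rate is given. It makes 60% against 45% a pessimistic case. A reader might go further and infer a serious bias: 60% against 30% would give 0.16–0.36 SD. Nothing in the documents supports such rates, or a 30-point effect of one infusion on stay.

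Second, two draws restricted to patients present at 24 hours fit a preoperative first sample and a second at about 24 hours. This also stands as a possible intention. A reader might infer from the rule that both draws follow the infusion and that change from baseline cannot be derived. That is one reading of untimed draws, not something the protocol states. Yet the rule needs rewording on either reading: a preoperative draw cannot depend on a stay not yet observed.

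Third, listing length of stay as an outcome does not show that the trial expects ketamine to change it. Correct: the documents show only that the possibility is being tested.

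Fourth, the outcome is marginal: exploratory in Protocol 8C and absent from the SAP's list. This limits the weight of the point but does not answer it, because the blood is still to be drawn and the markers are still a named protocol outcome.

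**Conclusion.** The point holds as a flaw of modest size in a secondary, exploratory outcome. The sampling rule conditions on something observed after randomization and treatment, and no pre-infusion sample is assured. Selection bias is probably small: zero if ketamine does not alter who stays, and about 0.05–0.17 SD in the two unequal cases tabulated, against detectable differences of about 0.9–1.2 SD. The more dependable loss is precision, 0.96 SD against 0.83–0.69 SD at 18 vs 16, and it arises if no baseline value is taken or if one is taken and not used as a covariate. The stay rates and both correlations are assumptions; the documents supply none of them. The primary MADRS comparison, response and remission are not affected.

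**What to change.** In Protocol 8D, state that sample 1 is taken on Day 0 before the study infusion and sample 2 at one fixed time after it, for example the Day 1 visit. Offer sampling on planned overnight admission, recorded before randomization, in place of actual stay. Add both draws to the day lists and the Study Procedures Matrix. In the SAP, add the markers to the outcome list, compare the randomized arms with the pre-infusion value as covariate, and report the numbers sampled and missing by arm.

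The blood burden is unchanged: two 10 mL draws. There are two costs. Patients discharged earlier than planned will have sample 1 without sample 2, so selection is reduced and not removed. And the trial was well advanced: SAP 4c puts the October 2021 revision at 75% of target enrolment (0.75 × 40 = 30 participants), so some participants may already have been sampled under the existing rule. The report should then say how many were sampled under each scheme.
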